10.2 Statistical analysis

The primary endpoint of the study is the proportion of patients achieving mRS ≤ 2 at 90 \pm 14 days after stroke onset. The proportion of patients achieving the primary endpoint will be calculated for each group, along with the rate difference (RD) and its 95% confidence interval (CI). A log-binomial model with a log-link function will be used to adjust the rate difference for multiple covariates, including age, pre-stroke mRS, time from onset to randomization, stroke severity (baseline NIHSS), and collateral circulation status (baseline PC-CS). The adjusted RD and its 95% CI will be reported.

For the shift analysis of mRS scores, a logistic ordinal regression model will be applied to calculate the common odds ratio (cOR) and its corresponding 95% CI.

The primary analysis will follow the intention-to-treat (ITT) principle. The main analysis will be based on a modified ITT population (m-ITT), defined as patients who were randomized and received treatment. Analyses will be conducted according to the original randomization group. Other populations, such as the as-treated set (ATS) and per-protocol set (PPS), will be used for sensitivity analyses. Details of the specific analytical methods and

population definitions can be found in the Statistical Analysis Plan (SAP).

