#### 3.2.2 Reporting standards for analysis results

The ITT, m-ITT, and PPS datasets will be analyzed according to the randomized treatment groups, while the AT and SS datasets will be analyzed based on the actual interventions received. Issues related to cases or data handling not explicitly described in the clinical trial protocol will be resolved following case discussions.

Continuous variables will be described using the mean, standard deviation, median, quartiles, minimum, and maximum values. Categorical and ordinal data will be summarized using frequencies and percentages. Statistical measures and the number of decimal places will be reported as outlined in the table below:

Name	Description	Decimal Places (dp)
Quantitative Data		
N	Number of subjects without missing results	0 dp
Mean	Arithmetic mean	Raw data decimal places + 1 dp

SD	Standard deviation	Raw data decimal places + 1 dp
Median	Median value	Raw data decimal places
Q1	25th percentile (first quartile)	Raw data decimal places
Q3	75th percentile (third quartile)	Raw data decimal places
Min	Minimum value	Raw data decimal places
Max	Maximum value	Raw data decimal places
Missing	Number of missing cases	0 dp; if the percentage frequency is less than 0.1%, the percentage will be displayed to the first non-zero digit. For example, if the percentage is "0.000523%", it will be displayed as "0.0005%" instead of "0.0%".
Qualitative (Categorical and Ordinal) data		
n	Number of subjects with a specific evaluation indicator value	0 dp
%	Percentage (0-100%)	1 dp
Statistical measures		
95% CI	95% confidence interval	Raw data decimal places + 2 dp

The comparison of baseline characteristics between the two groups will be conducted using appropriate statistical methods according to the type of data. For quantitative variables, an independent samples t-test will be used if normality and homogeneity of variance are satisfied; otherwise, the Wilcoxon rank-sum test will be applied. For categorical data, a chi-square test will be used if all expected cell counts are  $\geq 5$ , a continuity-corrected chi-square test will be used if one expected cell count is between 1 and 5, and Fisher's exact test will be applied if more than one expected cell count is between 1 and 5, or if any expected cell count is  $< 1$ . For ordinal data, the Wilcoxon rank-sum test will be used without adjusting for center effects, while the Cochran-Mantel-Haenszel (CMH) test will be applied if adjustments for center effects are needed.

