**2) End date of CM:**

- If the year and month are known, the last day of the known month will be used.
- If only the year is known, December 31 of that year will be used.
- If the imputed end date is after the last study visit date, the last study visit date will be used as the end date.

- If the year, month, and day are all missing, no imputation will be performed for the end date.

If the relationship between an AE and the study drug is missing, the AE will be classified as drug-related for the purpose of summary reporting.

For all other missing data in this study, no imputation will be performed, and the data will be analyzed and described in their original state as collected.

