#### 3.9.1 Primary efficacy endpoint

The primary efficacy endpoint, "the proportion of patients with mRS  $\leq 2$  at 90 days after onset," will be statistically described by treatment group. The 95% confidence intervals (CIs) will be calculated using the exact Clopper-Pearson method. Additionally, a bar chart will be used to display the distribution of mRS scores.

When using a superiority hypothesis test, the specific statistical hypotheses are as follows:

Null hypothesis  $H_0: p_T - p_C \leq 0$

Alternative hypothesis  $H_1: p_T - p_C > 0$

$\alpha = 0.025$  (one side)

If the hypothesis is adjusted to a non-inferiority hypothesis after the interim analysis, the specific statistical hypotheses are as follows:

Null hypothesis  $H_0: p_T - p_C \leq -15\%$

Alternative hypothesis  $H_1: p_T - p_C > -15\%$

$\alpha = 0.025$  (one side)

Here,  $p_T$  represent the proportions of patients with mRS  $\leq 2$  in the IVT followed by EVT and EVT alone groups, respectively.

A log-binomial model will be used, assuming the primary endpoint follows a binomial distribution. A log-link function will be applied, with covariates including age, pre-stroke mRS, time from onset to randomization, stroke severity (NIHSS score), and collateral circulation. Adjusted and unadjusted risk difference (RD) and risk ratio (RR) with their 95% confidence intervals will be reported.

For superiority, if the lower bound of the 95% CI of the adjusted RD  $> 0$ , superiority is established.

For non-inferiority, if the lower bound of the 95% CI of the adjusted RD  $> -15\%$ , non-inferiority is established.

Additionally, Chi-square tests (expected cell count  $\geq 5$ ), continuity-corrected chi-square tests (1 expected cell count between 1 and 5), or Fisher's exact test ( $\geq 1$  expected cell count  $< 5$  or any expected cell count  $< 1$ ) will also be used for group comparisons, and P-values will be reported.

The mRS score used in the primary analysis will be based on centralized assessments. If centralized assessments are missing for certain subjects, local investigator assessments will be used by default. Sensitivity analyses will also use local assessments to evaluate the robustness of the results.

A list of all primary efficacy endpoint data for all visits (m-ITT, AT, PPS sets) will be provided.

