#### 3.9.2 Secondary efficacy endpoints

The secondary efficacy endpoints are as following:

- (1) Proportions of patients with mRS = 0 or 1 at 90 days after stroke onset.
- (2) Proportions of patients with mRS = 0–3 at 90 days after stroke onset.
- (3) mRS score at 90 days after stroke onset.

(4) NIHSS score at 18–24 hours after procedure, 24–74 hours after procedure, and 5–7 days after stroke onset and their changes from baseline.

(5) Proportions of patients with a NIHSS score = 0 or 1, a NIHSS score = 0–2, a NIHSS score improvement  $\geq 4$  points, and a NIHSS score improvement  $\geq 8$  points at 18–24 hours after procedure, 24–74 hours after procedure, and 5–7 days after stroke onset.

(6) Glasgow coma scale score (GCS) at 18–24 hours after procedure, 24–74 hours after procedure, and 5–7 days after stroke onset and their changes from baseline.

(7) Barthel Index score (BI) and proportions of patients with BI = 95–100 at 30 and 90 days after stroke onset.

(8) EQ-5D-5L score at 90 days after stroke onset.

(9) eTICI score and successful reperfusion rates before and after EVT.

(10) mAOL score and recanalization rates at 24–72 hours after procedure.

(11) PC-ASPECTS score at 24–72 hours after procedure and 5–7 days after stroke onset.

(12) Lesion volume based on quantitative imaging detection at 24–72 hours after procedure and 5–7 days after stroke onset.

For categorical endpoints (1, 2, 5, 7, 9, and 10), proportions will be calculated with 95% CI using the exact Clopper-Pearson method. Group comparisons will use chi-square tests, continuity-corrected chi-square tests, or Fisher's exact test, as appropriate, and P-values will be reported. RD and RR with 95% CIs will also be calculated. Both unadjusted and adjusted results will be reported. Covariates include age, pre-stroke mRS, time from onset to randomization, NIHSS score, and collateral circulation.

For continuous endpoints (4, 6, 7, 8, 11, and 12), group comparisons will use independent samples t-tests (if normality and homogeneity of variance are satisfied) or Wilcoxon rank-sum tests (if not). Mean differences with 95% CIs will also be calculated. Both unadjusted and adjusted results will be reported. Covariates include age, pre-stroke mRS, time from onset to randomization, NIHSS score, and collateral circulation.

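### Both primary decisions rest on an adjusted risk difference, but the planned log-link model estimates a log risk ratio, and the plan gives no route to the difference, no interval method and no rule if the fit fails

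*Protocol*

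**What the plan says.** The Protocol Summary (Primary endpoint) and Protocol 10.2 name one adjustment model: "A log-binomial model with a log-link function will be used to adjust the rate difference for multiple covariates". The covariates are age, pre-stroke mRS, onset-to-randomization time, baseline NIHSS and collateral status. For the rest, Protocol 10.2 points onward: "Details of the specific analytical methods and" population definitions are to be found in the SAP.

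SAP 3.9.1 repeats the model: "A log-link function will be applied, with covariates including age, pre-stroke mRS, time from onset to randomization", followed by NIHSS and collaterals. It promises adjusted and unadjusted RD and RR with 95% intervals, and then sets the decision rules. "For superiority, if the lower bound of the 95% CI of the adjusted RD" exceeds 0, superiority is established. "For non-inferiority, if the lower bound of the 95% CI of the adjusted RD" exceeds -15%, non-inferiority is established.

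SAP 3.9.2 asks for the same measures for secondary binary endpoints without naming a model: "RD and RR with 95% CIs will also be calculated. Both unadjusted and adjusted results will be reported".

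**The concern.** With a log link, the treatment coefficient is the log of a risk ratio. The decision rules need a risk difference, so a further step is required, and so is an interval for its result. Neither is specified.

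The log link also needs every patient's linear predictor to stay at or below zero, or the fitted probability exceeds 1. With several prognostic covariates this constraint often binds, and the fit may then fail to converge or stop on the boundary. The plan has no rule for that case. The gap falls on the one analysis that decides the trial. If the model does not fit, someone must pick the deciding estimator with the outcome data in hand.

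**Working it through.** **1. The plan's own figures.** Superiority, unpooled variance: n = (1.960 + 0.8416)² × (0.4203×0.5797 + 0.2614×0.7386) / 0.1589² = 7.849 × 0.43672 / 0.025249 = 135.8, so 136 per group; 136/0.8 = 170. Non-inferiority (NI): n = 7.849 × 2 × 0.4203×0.5797 / 0.15² = 170.0, so 170 per group with 80.0% power. Both reproduce. Both work on the unadjusted RD scale, and the sample size is not at issue here.

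**2. The risk ratio does not fix the RD.** RD = reference risk × (RR − 1). The design RR is 0.4203/0.2614 = 1.608. This gives an RD of 9.1 points at a reference risk of 15%, 15.9 at 26.14%, 18.2 at 30% and 25.5 at 42.03%. The set of patients over which the RD is evaluated must therefore be stated.

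**3. Where the missing step might be.**
- Clopper-Pearson (SAP 3.9.1) gives an interval for a single proportion, not for an adjusted RD.
- The chi-square and Fisher tests (SAP 3.9.1) are additional P-values for no difference. They cannot assess a -15% margin.
- The unadjusted RD is reported, but no rule lets it decide.
- SAP 3.2.1 names SAS 9.4 or later, but no procedure or fitting option.
- SAP 3.2.2 has only a general clause: "Issues related to cases or data handling not explicitly described in the clinical trial protocol will be resolved following case discussions". It names no method and would itself operate after the data are seen.
- SAP section 4 refers to a TFL shell that was not among the supplied documents.

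**4. Does the model fit?** The documents give no covariate effects, so these are assumed. n = 340, 1:1. Age N(65,12); pre-stroke mRS 0/1/2 at 80/13/7%; time uniform 1–4.5 h; NIHSS 6 + gamma(2, scale 8), capped at 42; PC-CS N(6,2), rounded to 0–10. Log-odds per SD: age -0.4, mRS -0.3, time -0.2, NIHSS -1.0, PC-CS +0.4, multiplied by 0.25 (weak), 0.5 (moderate) or 1.0 (strong). A second outcome model, which favours the plan, uses a log link with these coefficients times 0.6 and probabilities capped at 0.97. NI null: EVT alone 27.03%, IVT plus EVT 42.03%, 5,000 trials per cell.

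Log-binomial fit failed, or reached the boundary, in % of trials (weak/moderate/strong):

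| Routine | Logistic outcomes | Log-link outcomes |
|---|---|---|
| Constrained ML, on boundary | 3/23/89 | 2/30/99 |
| IRLS, intercept start | 5/40/99 | 4/40/>99 |
| IRLS, default start | 41/86/>99 | 37/84/100 |

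A repeat with 1,500 trials per cell (logistic outcomes) gave 5/42/99.5% from an intercept start and 51/95/100% from a data-based start. Standardised logistic regression had no failure in 48,000 trials (30,000 under the NI null, 9,000 under superiority, 9,000 under the NI alternative).

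**5. What the choice does to the decisions** (%, weak/moderate/strong). The NI contrast is EVT alone minus IVT followed by EVT. True RD is -15 points for NI error (nominal 2.5%). Rates are 42.03 vs 26.14% for superiority power and 42.03% in both arms for NI power, with 3,000 trials per power cell.

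| RD estimate | NI error, logistic outcomes | NI error, log-link outcomes | Superiority power | NI power |
|---|---|---|---|---|
| Standardised logistic, HC3 | 2.3/2.2/2.2 | 2.4/2.2/1.9 | 86.6/88.5/92.2 | 79.1/80.7/86.6 |
| Log-binomial averaged, logistic fallback | 3.0/3.2/3.0 | 2.8/2.6/2.0 | 87.5/88.0/90.5 | 80.8/83.6/86.9 |
| Unadjusted | 2.4/2.4/2.3 | not tabulated | 86.8/87.3/87.1 | 78.6/78.8/79.8 |

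Monte Carlo SE is about 0.2 points for the error rates and 0.5–0.8 for power. Repeats of 1,500 trials put the logistic HC3 error between 1.9 and 2.7%.

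The first two methods reach different decisions in 0.8/1.4/0.9% of trials under the NI null, 2.1/2.9/2.1% under superiority and 3.8/5.0/1.1% under the NI alternative.

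Trials in which the log-binomial model fits are not a random subset. Among interior constrained-ML fits (4,870, 3,852 and 551 of 5,000) the averaged RD was -14.9/-14.1/-11.4 points at a true -15, and NI error was 3.1/3.9/9.3%. A pre-specified fallback brings this to the 3.0/3.2/3.0% in the table.

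**The case against.** The strongest reply is that this is a missing specification and not a wrong analysis. That stands. A reader might infer that an RD cannot come from a log-link model. It can, by averaging predicted risks, and the averaged log-binomial and logistic RDs perform almost alike. Superiority, the primary hypothesis, is little affected.

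The failure rates rest on covariate effects and fitting routines that appear nowhere in the documents, and none of the fits was run in SAS. They run from 2% to 100% and do not predict this trial. A boundary solution is also not the same as non-convergence: in a 400-trial check per cell, the constrained optimiser converged every time. With strong effects, however, the averaged RD from those fits was about -11.7 against a true -15, so a boundary rule is still needed.

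A reader might infer that the trial's NI error is inflated by the amounts above. The documents do not support that. NI is tested only if the arms look similar at the interim, and the error figures ignore this gate. If similar means within 3, 5 or 10 points (the plan does not define it), with 57 per arm at the interim and an unadjusted Wald test at 170 per arm, a switch followed by false NI occurs in 0.6, 1.0 or 1.9% of trials at a true -15. A reader might also suppose that the RD would be evaluated at mean covariate values, which would make NI easier to declare. No section suggests that reading.

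Blinded outcome assessment and the promised unadjusted RD would make a selective choice more visible. They do not say which estimate decides.

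**Conclusion.** The gap is real and lies in the text. Both decisions use the lower bound of an adjusted RD, the only model named estimates a log risk ratio, and the supplied documents give no derivation, no interval and no non-fit rule. That finding rests on no simulation assumption; it is limited to the supplied sections, since the TFL shell could hold more.

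Its practical size depends on assumed covariate effects. Trouble with the fit is rare, about 3–5%, if effects are weak and the routine is good. It reaches 40% or more with moderate effects and unconstrained fitting, and about 90% or more with strong effects. Standardised logistic regression always fitted, with an ungated NI error of about 2–2.7%. Its advantage is that it fits reliably and is averaged over patients, not the logit link itself. The method should be fixed before the final data are unblinded. The sample size and the superiority test are not called into question.

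**What to change.** In the Protocol Summary, Protocol 10.2 and SAP 3.9.1, replace the log-binomial sentence with text such as:

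> The adjusted RD and RR come from logistic regression on treatment and the same five baseline covariates, by marginal standardisation: each m-ITT patient's outcome probability is predicted under each arm and averaged over the m-ITT set. The 95% CI of the RD is the delta-method interval with HC3 robust variance. Both decision rules apply to this RD. If the model cannot be fitted (non-convergence or separation), the unadjusted RD with its 95% Wald CI decides.

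Equally acceptable: keep the log-binomial model, name its SAS procedure and fitting options, average its RD over the m-ITT set with a robust delta-method interval, and pre-specify the standardised logistic RD as the fallback on non-convergence or when a fitted probability reaches 1.

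Either way, state the same method in SAP 3.9.2 for the adjusted RD and RR of secondary binary endpoints.

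The cost is rewording and minor programming, to be validated in SAS. No extra data, covariates or patients are needed. The HC3 interval is slightly conservative (1.9–2.4% against 2.5% in the 5,000-trial runs). Compared with the log-binomial option, the logistic option has NI power lower by 1.7, 2.9 and 0.3 points (weak, moderate, strong effects); superiority power differs by -0.9, +0.5 and +1.7.

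The direction of the NI contrast needs separate reconciliation: SAP 1.5 defines p_T as IVT followed by EVT, while the protocol tests whether EVT alone is non-inferior.

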8.1.4 Additional study parameters

Baseline parameters to be recorded include demographic data such as age, sex, ethnicity, and body mass index, as well as clinical histories, including prior stroke, comorbidities (e.g., hypertension, diabetes, atrial fibrillation, and myocardial infarction), smoking, alcohol consumption, prior medications (e.g., antiplatelets and anticoagulants), and vital signs (e.g., blood pressure, temperature, pulse, and respiration rate). Neurological assessments include pre-stroke mRS, NIHSS, and GCS scores. Clinical laboratory tests include INR, APTT, platelet count, and blood glucose levels. Imaging results will include PC-ASPECTS, PMI (Pons-midbrain index; **Appendix 13**), PC-CS (Posterior circulation collateral score; **Appendix 14**), and BATMAN (Basilar artery on CT angiography; **Appendix 15**) scores.

We will document the actual dose, type, route, and administration time of IVT medications. Additionally, we will record the time intervals from symptom onset to emergency department arrival, CT/MR/DSA imaging, randomization, IVT initiation, EVT procedure initiation, reperfusion, and EVT procedure completion. Details of endovascular devices, including model, specifications, quantity, and usage sequence, as well as type of anesthesia and sedatives (if used), will also be recorded.

Patients included in this trial are recruited from two main pathways: (1) direct referrals from external healthcare facilities and (2) direct admissions to the comprehensive stroke center (Mothership model). This recruitment strategy reflects typical clinical practice and ensures the inclusion of a diverse patient population.

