10.1 Sample size calculation

Currently, no large-scale RCTs exist in this field. The sample size calculation for this study is based on the results of the RESCUE-RE registry study in the Chinese population^[25], which reported that the proportion of patients achieving a mRS score ≤ 2 at 90 \pm 14 days post-procedure was 42.03% in the IVT followed by EVT group and 26.14% in the EVT alone group. Based on the superiority hypothesis, the study aims to determine whether the favorable outcome rate (90-day mRS ≤ 2) in the IVT followed by EVT group is superior to that in the EVT alone group. Assuming a one-sided type I error rate of 0.025 and 80% statistical power, and using a 1:1 randomization ratio, the required sample size is 136 patients per group (a total of 272 patients). Considering an anticipated dropout rate of approximately 20%, the final sample size is adjusted to 340 patients, with 170 patients per group.

This study hypothesizes that IVT followed by EVT is superior to EVT alone. However, given the limited reference data and clinical evidence in the anterior circulation indicating that EVT alone may be non-inferior to IVT followed by EVT, an interim analysis is planned after one-third (114) of the patients have completed follow-up for the primary endpoint. During the interim analysis, the DSMB will evaluate the efficacy data from both groups and conduct a sample size re-estimation based on the conditional power calculated from the available data. The DSMB will provide recommendations to the BEST-BAO research team on adjustments to the sample size or modifications to the study hypothesis.

If the efficacy advantage of the IVT followed by EVT group over the EVT alone group is less than anticipated, the sample size may be expanded appropriately, with an upper limit of no more than 20% of the original sample size. If the efficacy of the two groups appears to be similar, the study design will shift to a non-inferiority framework, evaluating whether EVT alone is non-inferior to IVT followed by EVT. Assuming similar efficacy (with both groups achieving a 90-day mRS score ≤ 2 in 42.03% of patients), the current sample size of 170 patients per group provides 80% power to test non-inferiority, with a one-sided type I error rate of 0.025 and a non-inferiority margin of -15%. The interim analysis and sample size re-estimation will be conducted under the strict control of the DSMB to ensure that the type I error rate is not inflated.

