10.3 Subgroup analyses

Subgroup analyses of the primary endpoint will be conducted based on the following variables:

- (1) Age
- (2) Sex
- (3) Medication history
- (4) Pre-stroke mRS score
- (5) Baseline stroke severity (NIHSS score)
- (6) Blood glucose level at admission
- (7) Baseline infarct size (PC-ASPECTS score and quantitative measurement)
- (8) Baseline collateral circulation status (PC-CS and BATMAN scores)
- (9) Stroke etiology
- (10) Location of basilar artery occlusion
- (11) Time from symptom onset to randomization
- (12) Time from randomization to groin puncture
- (13) Time from randomization to guiding catheter insertion into the vascular puncture sheath
- (14) Time from randomization to cerebrovascular reperfusion

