Appendix 20. Imaging requirements

Baseline Imaging minimum requirements

When

Prior to randomization, a CT/CTA, MRI/MRA, or CT/DSA should be performed to assess eligibility criteria.

How

1. Pre-randomization CT:

(1) Positioning and scope: The patient should lie in a supine position, with both sides of the head symmetrically aligned. The external auditory meatus on both sides should be equidistant from the table, and the chin should be slightly tucked. Scanning should cover a continuous range of 100–120 mm from the baseline upwards.

(2) Scan reference line: Use the standard orbitomeatal line (a line between the outer canthus of the eye and the external auditory canal). This line roughly parallels the skull base, minimizing bone artifacts and improving visualization of posterior fossa structures.

(3) Tube voltage: 120 kV.

(4) Tube current: 200–300 mA.

(5) Slice thickness and interval: Standard slice thickness of 5–8 mm, with an interval of 5–8 mm.

(6) Window width and window level: Brain window: level = 30–40 HU, width = 70–100 HU. Bone window: level = 250–500 HU, width = 1000–1600 HU. Bone windows typically use a bone algorithm.

2. Pre-randomization CTA:

(1) CTA coverage: It is recommended that the CTA cover the entire region from the aortic arch to the top of the head.

(2) Procedure: Contrast agent: Use a non-ionic, iso-osmolar iodine contrast agent with a concentration of 300 mgI/dL, with a total volume of 90 ml. Injector settings: Set the flow rate at 4 ml/second for the first 30 ml, followed by 3 ml/second for the remaining 60 ml. Scanning: Start the CTA scan simultaneously with the high-pressure injector, guided by Bolus tracking software to ensure optimal timing. The scan range should extend from the aortic arch to the cranial vertex. Use a tube voltage of 120 kV, tube current of 150 mA, slice thickness of 0.5–1.5 mm, and set the reconstruction interval to half of the slice thickness.

(3) Image processing: Image Processing: Provide at least one Maximum Intensity Projection (MIP) image from the CTA data set to assess vascular parameters. Generate three-dimensional volume rendering (VR) and three-dimensional MIP images for vascular visualization. Pay special attention to the original CTA data, particularly the bilateral subclavian arteries and vertebral arteries.

(4) CTA original images: Reconstruct the original CTA images with a slice thickness of 10–12 mm to evaluate the presence of acute infarct lesion.

3. Pre-randomization MRI/MRA:

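### The deciding adjusted risk difference leaves out baseline PC-ASPECTS, which is already collected and centrally read; adding it would be a small gain in precision and robustness, not the correction of a bias.

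*Protocol*

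**What the plan says.** Protocol 10.2 adjusts the primary RD for covariates "including age, pre-stroke mRS, time from onset to randomization, stroke severity (baseline NIHSS), and collateral circulation status (baseline PC-CS"). The Protocol Summary repeats this list. SAP 3.9.1 fits the model "with covariates including age, pre-stroke mRS, time from onset to randomization, stroke severity (NIHSS score), and collateral circulation" and declares superiority or non-inferiority from the lower 95% limit of the adjusted RD, so the covariate list bears on the decision itself. Neither document lists a measure of infarct extent or explains its absence.

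The plan does collect one:

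- Protocol 8.1.4: "Imaging results will include PC-ASPECTS" at baseline, along with other scores. The visit schedules in both documents agree.
- Protocol 8.1.6 has PC-ASPECTS determined on CT or MRI-DWI. All imaging goes to a blinded central committee with two readers and a senior reader for discrepancies.
- Appendix 20: "Prior to randomization, a CT/CTA, MRI/MRA, or CT/DSA should be performed to assess eligibility criteria". Each of these routes contains a CT or an MRI, and inclusion criterion 3 requires one of them to rule out haemorrhage.
- Protocol 10.3 and SAP 3.9.3 list "Baseline infarct size (PC-ASPECTS score and quantitative measurement") as a subgroup factor for the primary endpoint.

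SAP 3.2.3 imputes the 90-day mRS. Apart from dates and AE relatedness it imputes nothing else, so a missing covariate stays missing.

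**The concern.** NIHSS and collateral status describe the deficit and the reserve supply. Neither records how much brainstem, cerebellar and posterior cerebral territory has already infarcted. If that extent predicts 90-day mRS over and above the five covariates, some outcome variation that could be explained before treatment stays in the error of the deciding estimate, and a chance difference between arms in infarct extent is only partly adjusted away. Eligibility sets no PC-ASPECTS limit, and the text names no stratification or minimisation factor.

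A small gain is worth having because the non-inferiority branch has no slack. Its 80% power needs all 170 randomised patients per group, and the sample-size increase is capped at 20%. The choice also has to be made in advance, because an adjustment added after unblinding could not carry the decision.

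**Working it through.** **Reproducing the plan's figures.** Protocol 10.1 gives success rates of "42.03% in the IVT followed by EVT group and 26.14% in the EVT alone group" and the design: "Assuming a one-sided type I error rate of 0.025 and 80% statistical power, and using a 1:1 randomization ratio". The unpooled formula gives

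n = (1.960 + 0.842)² × [0.4203×0.5797 + 0.2614×0.7386] / 0.1589² = 135.76, rounded up to 136.

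This matches "the required sample size is 136 patients per group (a total of 272 patients"). Then 272/0.8 = 340. For non-inferiority with both rates at 42.03% and a 15-point margin, n = 170 per group. These are unadjusted calculations, so the stated power does not depend on the covariate list.

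**Assumptions (not in the documents).** The five covariates are summarised as one prognostic score with an odds ratio of 2.0 or 2.5 per SD. PC-ASPECTS correlates 0.3 or 0.5 with that score. Its own conditional odds ratio, per SD in the favourable direction, is 1.0, 1.2, 1.5 or 2.0. If the SD were 1.5 points, 1.5 per SD would be about 1.3 per point, since 1.3^1.5 = 1.48. The plan does not say how an RD is obtained from the log-link model, so the calculation uses a logistic model standardised to the RD scale.

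**Variance.** With 1:1 allocation, total N, and covariate-predicted risks m1 and m0 in the two arms,

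N × Var(RD) = 2[p1(1−p1) − Var(m1)] + 2[p2(1−p2) − Var(m0)] + Var(m1 − m0)

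Power = Φ(0.1589/SE − 1.96)

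Unadjusted, SE = √(0.4367/136) = 5.67 points and power is 80.1%. With existing-score odds ratio 2.0, correlation 0.3 and N = 272:

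| PC-ASPECTS OR per SD | Variance cut | SE, five covariates → with PC-ASPECTS (points) | Power | Worth in patients | 95% imbalance shift (points) |
|---|---|---|---|---|---|
| 1.0 | 0% | 5.41 → 5.41 | 83.6% → 83.6% | 0 | 0 |
| 1.2 | 0.6% | 5.38 → 5.36 | 84.0% → 84.2% | 1.7 | 0.8 |
| 1.5 | 2.9% | 5.34 → 5.27 | 84.4% → 85.5% | 7.8 | 1.7 |
| 2.0 | 7.6% | 5.32 → 5.11 | 84.8% → 87.5% | 20.8 | 2.8 |

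Across all 16 scenarios the cut is 0 to 7.6% and the power gain 0 to 2.7 points. A correlation of 0.5 gives smaller cuts (6.2 to 6.3% at OR 2.0). Because missing mRS values are imputed, the analysed number may be nearer 340; there the gain is 0 to 1.8 points.

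**Chance imbalance.** The arm difference in a standardised score has SD √(4/272) = 0.121. The fraction not shared with the existing score is √(1 − 0.3²) = 0.954. At OR 1.5 the risk slope is 0.076 per SD, so the 95% shift is 1.96 × 0.121 × 0.954 × 0.076 = 0.017, or 1.7 points.

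This is the variance gain seen another way and should not be added to it: (1.7/1.96)² / 5.34² is about 2.6%, in line with the 2.9% above.

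**Simulation.** With 3,000 trials per setting (existing score OR 2.0, correlation 0.3), the empirical SD of the RD fell from 5.41 to 5.22 points at OR 2.0, with power rising from 82.8% to 85.8%. At OR 1.2 nothing visible changed (5.36 and 5.34; 83.8% and 83.6%). A separate simulation at 272 patients that added both PC-ASPECTS and the modality indicator gave anything from about a 1% variance increase to a 5% reduction.

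**The case against.** The strongest reply is that this is a preference. The plan pre-specifies five sensible covariates, omitting a sixth contradicts nothing in the documents, and the sample size stands without any adjustment. That is correct, and it sets the weight of the point.

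Four stronger readings are tempting, and the documents do not support them:

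- **That precision is lost.** The documents give no SD for PC-ASPECTS, no correlation with NIHSS and no prognostic strength. The assumed range includes zero. Entry within 4.5 hours of onset may also narrow the spread of scores.
- **That an imbalance passes straight into the RD, or biases it.** NIHSS and the other covariates absorb the shared part. What remains is chance variation that the confidence interval already covers, and unconditional type I error is unaffected. Nor should the point rest on unstratified randomisation: the text names no factor, but the Appendix 16 flowchart cited in Protocol 8.2 was not visible in the copy reviewed.
- **That PC-CS, the imaging covariate chosen, is available only with CTA.** Appendix 14 scores several arteries on CTA, but Protocol 8.1.6 allows CTA, MRA or DSA.
- **That the change is free.** CT and DWI readings would be pooled. An unread scan could drop a patient, since covariates are not imputed. A log link does not hold fitted risks below 1, so the model may already be hard to fit before two terms are added.

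Both lists open with a form of the word include, so they are not expressly closed. That does not help much: a model that decides the trial needs a closed list.

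**Conclusion.** The omission is real in both documents, and the variable is collected, centrally read and scoreable in every patient by design. The primary analysis as written remains valid. Under conditional odds ratios of 1.0 to 2.0 per SD, adding PC-ASPECTS is worth about 0 to 8% of the variance of the RD, an SE reduction of at most about 0.2 points, and 0 to about 2.7 power points at 272 patients. The residual imbalance shift it would remove is up to about 1.7 points at OR 1.5 per SD (2.8 at OR 2.0), against an SE of about 5.3. These sizes rest on assumed prognostic strengths and on a logistic model standardised to the RD, not on the log-link fit the plan specifies. This is an optional improvement, and nothing else in the design depends on it.

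**What to change.** Before unblinding, add baseline PC-ASPECTS as a continuous term, with an indicator for CT versus MRI-DWI reading, to the covariates of the adjusted primary RD in the Protocol Summary, Protocol 10.2 and SAP 3.9.1. Add the same terms to the adjusted mRS shift model in SAP 3.9.2. In SAP 3.2.3, state a rule for missing baseline scores, for example imputing the overall mean without regard to treatment arm, so that no patient drops out of the deciding model.

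No new data are needed. The cost is two more parameters against about 93 expected successes in 272 patients (136 × 0.6817) or 116 in 340 (170 × 0.6817), in a log-link model that may already have fitting difficulty. The gain may be nil if PC-ASPECTS adds little beyond NIHSS. If the team prefers to keep the deciding model as it is, a pre-specified sensitivity analysis with PC-ASPECTS, or a sentence justifying its omission, would be a reasonable minimum.
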